#### **6.4.3.3. Medication and Medical History**

A complete medical history will be taken during Study 0170 and will include evaluation of past and present cardiovascular, respiratory, GI, renal, hepatic, neurological, endocrine, lymphatic, hematologic, immunologic, dermatologic, psychiatric, genitourinary, substance abuse, surgical history, or any other diseases or disorders. Medical conditions will be recorded for 2 years prior to screening visit, along with the date of diagnosis, and any other relevant medical history that has an impact to the subject.

Medical events or conditions that arise or worsen in severity or frequency after date of first dose of study drug will be recorded as an AE in Study 0171.

#### **6.4.3.4. Physical Examination**

An abbreviated physical examination will be performed by an appropriately qualified individual (e.g., physician, nurse practitioner, physician's assistant, or equivalent, under the supervision of a physician) and will include examination of the following: general appearance; skin; head, ears, eyes, nose, and throat; neck; cardiovascular system; respiratory system; abdomen/ GI system; extremities; lymphatic system (lymph nodes); and nervous system. Physical examinations, at the discretion of the Investigator, can be abbreviated and symptomatic, largely focused on evaluation of AEs, if any, and any abnormalities identified.

#### **6.4.3.5. Neurological Examination**

Any abnormalities identified at Visit 1 will be recorded as neurological medical history. Any abnormalities or symptoms reported during treatment that arise or worsen in severity or frequency will be reported as AEs.

The examination will assess the following:

- Cranial nerves (cranial nerves II-XII, excluding funduscopic examination)
- Motor system (tone, strength, and abnormal movements)
- Sensory system (light touch, pinprick, joint position, and vibration)
- Reflexes (deep tendon reflexes and plantar responses)
- Coordination (upper and lower extremities)
- Gait (base and tandem gait)
- Station (posture and stability)

#### **6.4.3.6. Vital Signs**

The HR, BP, RR, and body temperature will be recorded according to the Schedule of Study Procedures ([Table 1](#)).

The vital sign measurements (BP and HR) should be performed after the subject has rested sufficiently as determined by the appropriate staff. Subject position, measurement device, and arm (left vs. right) should be kept consistent throughout the study. Blood pressure will be measured using a calibrated manual or automatic BP device.

Heart rate will be recorded by palpation of the radial pulse over at least a 30-second period or by the automated BP device.

Body temperature will be measured and reported in degrees Celsius. The method used to collect temperature can be either oral or tympanic but should be consistent throughout the subject's participation.

Any vital sign outside the normal range may be repeated at the discretion of the Investigator. Collection of additional vital sign measurements for routine safety monitoring at additional time points or study days may be performed at the discretion of the Investigator, or upon request by the sponsor.

#### **6.4.3.7. Electrocardiograms**

The 12-lead ECGs will be recorded in triplicate and separated by at least 1 minute for each replicate, according to the Schedule of Study Procedures ([Table 1](#)), after the subject has been resting at least 5 minutes in the seated or supine position before the first reading. Actual time of the assessment must be recorded for each iteration. The corrected QT interval using the Fridericia's formula (QTcF) will be used. The ECGs should be reviewed on the visit day at the site to allow for any appropriate action, if required.

#### **6.4.3.8. Incidence of Falls Diary**

Falls in subjects with symptomatic nOH are common and potentially catastrophic. They can lead to serious injuries including hip fractures or head trauma; furthermore, fear of falling can limit mobility and physical activity. Thus, incidence of patient-reported falls is being captured in a diary. Assessments will be performed as specified in the Schedule of Study Procedures ([Table 1](#)). An example of the diary is provided in [Appendix 2](#).

#### **6.4.3.9. Laboratory Tests**

Laboratory tests will be performed as specified in Schedule of Study Procedures ([Table 1](#)).

Additional and repeat laboratory safety testing for the evaluation of abnormal results and/or AEs during the study may be performed at the discretion of the Investigator or upon request of the sponsor.

Detailed instructions and collection kits for sample collection, handling, and shipping will be provided in the laboratory manual.

##### **6.4.3.9.1. Hematology**

Hematology samples will be analyzed for the following: hematocrit and hemoglobin; red blood cell count; mean corpuscular volume; mean corpuscular hemoglobin; white blood cell count, including differential count (percent and absolute) of neutrophils, eosinophils, basophils, monocytes, lymphocytes; and platelet count.

#### 6.4.3.9.2. Serum Chemistry

Chemistry samples will be analyzed for the following: sodium, potassium, calcium, chloride, bicarbonate, glucose, blood urea nitrogen, creatinine, total protein, albumin, alkaline phosphatase, ALT, AST, bilirubin, lactate dehydrogenase, and creatine phosphokinase.

#### 6.4.3.9.3. Urinalysis

Urinalysis includes determination of specific gravity; presence of blood, protein, and leukocytes; and microscopic examination of sediment, if clinically indicated.

#### 6.4.3.9.4. Unscheduled Visit

All sites are allowed, at Investigator discretion, to conduct either in clinic or remote unscheduled visit(s) for subject safety or unexpected subject medical needs outside of the regular visit schedule. In this case, unscheduled visits are not considered protocol deviations and the Investigator is not required to obtain pre-approval from the Sponsor. Data collected during these visits may include any protocol-specified assessments which will be captured in the clinical database.

### 6.5. Concomitant Medications

Subjects should not have changed dose, frequency, or type of prescribed medication for orthostatic hypotension within 7 days prior to Week 0.

[REDACTED]

#### 6.5.1. [REDACTED]

[REDACTED]

#### 6.6. [REDACTED]

[REDACTED]

[REDACTED]

**6.7.** [REDACTED]

[REDACTED]

■ [REDACTED]

■ [REDACTED]

■ [REDACTED]

■ [REDACTED]

■ [REDACTED]

■ [REDACTED]

**6.8. Discontinuation**

**6.8.1. Subject Discontinuation**

Any subject (or his or her legally authorized representative) may withdraw their consent to participate in the study at any time without prejudice. The Investigator must withdraw from the study any subject who requests to be withdrawn. A subject's participation in the study may be discontinued at any time at the discretion of the Investigator and in accordance with his or her clinical judgment. When possible, the tests and evaluations listed for the termination visit should be carried out. If a subject withdraws before completing the study, the reason for withdrawal is to be documented on the CRF.

The Sponsor will be notified of all subject withdrawals.

Reasons for which the Investigator or the Sponsor may withdraw a subject from the study or a subject may choose to terminate participation before completion of the study include, but are not limited to, the following:

- AE
- Subject choice
- Major violation of the protocol
- Termination of the study by the Sponsor
- Other

Subjects who discontinue study drug early because of an adverse reaction should be encouraged to continue their participation in the follow-up safety assessments. If a subject fails to return for scheduled visits, a documented effort must be made to determine the reason.

#### **6.8.2. Subject Replacement**

Subjects will not be replaced.

#### **6.8.3. Study Discontinuation**

The Sponsor reserves the right to discontinue this study at any time for any reason.

Periodic review of unblinded data by an external IDMC (Section 8.7) may lead to the board's recommendation of pausing dosing or terminating the study. In the event of premature study termination, best efforts to guarantee appropriate safety follow-up of subjects who have already been enrolled will be made and institutional review boards (IRBs) and the regulatory authorities will be informed.

#### **6.8.4. Dose Stopping Rules**

Any subject meeting 1 or more of the following stopping criteria will be required to immediately discontinue dosing with study medication and will subsequently be discontinued from participation in the study:

- [REDACTED]
- [REDACTED]
- [REDACTED]
- [REDACTED]

#### **6.9. Pregnancy**

TD-9855 has been shown to be non-genotoxic in a standard battery of genotoxicity assays (in vitro Ames and chromosomal aberration assays and in vivo micronucleus assay in rat). TD-9855 demonstrated effects on neonatal mortality and decreased rates of pup growth in the pre- and postnatal study in rats. Based on the NOAEL in reproductive-toxicology studies in preclinical species, there exists a greater than 100x margin between exposure in preclinical species at NOAEL vs. exposure in male and female patients at 4 weeks post stopping administration of [REDACTED] TD-9855 dose. Thus, application of pregnancy prevention measures for 30 days post last dose of TD-9855 is sufficient to address the risk of substantial drug exposure in semen or maternal circulation.

To confirm the absence of pregnancy in female subjects of childbearing potential, urine  $\beta$ hCG testing will be performed during specified visits, as listed in the Schedule of Study Procedures (Table 1). If the urine  $\beta$ hCG test is positive, a serum  $\beta$ hCG test must be performed. The pregnancy test must be confirmed negative for a subject to be eligible for this study unless the PI deems the test is falsely positive.

If a subject becomes pregnant while taking TD-9855, or during the 1 month after the last dose of treatment, the pregnancy must be reported to the sponsor's medical monitor (or designee) immediately (within 24-hours) by following the procedures for SAE reporting as outlined in Section 7.4.2. Study drug must be discontinued for any pregnant subject still on study drug treatment. Follow-up information regarding the outcome of the pregnancy and any postnatal sequelae in the infant will be required.

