### SCHEDULE OF STUDY PROCEDURES

**Table 1: Schedule of Study Procedures (Visits 1 – 6)**

Each study visit for each subject may be conducted either in clinic or remotely									
Study Week (Visit/Telephone):	Week 0 Visit 1 (0170 Visit 9)	Week 2 Visit 2 +/- 3 days	Week 6 Visit 3 +/- 3 days	Week 10 Visit 4 +/- 7 days	Week 14 Telephone 1 +/- 3 days	Week 18 Visit 5 +/- 7 days	Week 22 Telephone 2 +/- 3 days	Week 26 Visit 6 +/- 7 days	Early Termination up to Week 26
Informed Consent	X								
Inclusion / exclusion criteria	X								
Medical history, including smoking history	X								
Concomitant Medications	X a	X	X	X	X	X	X	X	X
C-SSRS	X a	X	X	X		X		X	X
[REDACTED]	[REDACTED]	[REDACTED]	[REDACTED]	[REDACTED]		[REDACTED]		[REDACTED]	[REDACTED]
Vital signs (heart rate, blood pressure, respiratory rate and body temperature)	X a, b	X b	X b	X b		X b		X b	X b
Physical examination	X a			X				X	X
Neurological examination	X a			X				X	X
12-lead electrocardiogram e	X a			X				X	X
Pregnancy Test	X a, c			X c				X c	X c
Safety Labs (chemistry, hematology, urinalysis)	X a			X				X	X
Dosing, Incidence of Falls, and Midodrine Diaries	X a	X	X	X		X		X	X
Adverse Events	X a	X	X	X	X	X	X	X	X
Dispense Study Drug	X d	X d	X d	X d		X d		X d	
Study Drug Dosing	X d								
Collect Study Drug		X	X	X		X		X	X

a. Study 0170 procedures conducted at Visit 9 will serve as the baseline assessment for Visit 1 of Study 0171.  
 b. Vital signs will be assessed after the subject has been resting for at least 5 minutes in the seated or supine position.

- c. In women of childbearing potential only, urine beta human chorionic gonadotropin ( $\beta$ hCG) test will be performed and if positive, confirmation with serum  $\beta$ hCG test is required. The pregnancy test must be confirmed negative for a subject to be eligible for this study.
- d. Study drug will be ingested in the morning at approximately the same time of day with 8 ounces of water. The exact time and day of dosing will be recorded on the mornings of study visits. Subjects must be reminded to maintain an adequate fluid intake during their scheduled visits. Subjects will start taking study drug on the day after Visit 1.

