**Table 2: Schedule of Study Procedures (Visits 7 – 14 Extension)**

Study Week (Visit/Telephone):	Wk 38 Visit 7 +/-7 days	Wk 50 Visit 8 +/-7 days	Wk 62 Telephone 3 +/-7 days	Wk 74 Visit 9 +/-7 day	Wk 86 Telephone 4 +/-7 days	Wk 98 Visit 10 +/-7 days	Wk 110 Telephone 5 +/-7 days	Wk 122 Visit 11 +/-7 days	Wk 134 Telephone 6 +/-7 days	Wk 146 Visit 12 +/-7 days	Wk 158 Telephone 7 +/-7 days	Wk 170 Visit 13 +/-7 days	Wk 182 Visit 14 End of Treatment Early Termination after Week 26 +/-7 days	Wk 184 Telephone 8 Follow-up +/-7 days
Procedure														
Concomitant Medications	X	X	X	X	X	X	X	X	X	X	X	X	X	X
Adverse Events	X	X	X	X	X	X	X	X	X	X	X	X	X	X
Pregnancy Test a		X		X		X		X		X			X	
Dispense Study Drug	X	X		X		X		X		X		X		
Study Drug Dosing	X b													
Collect Study Drug	X	X		X		X		X		X		X	X	

a. In women of childbearing potential only, urine beta human chorionic gonadotropin (βhCG) test will be performed.

b. Study drug will be ingested in the morning at approximately the same time of day with 8 ounces of water.

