### **4.3. Pregnancy and Contraception**

#### **4.3.1. Females of Childbearing Potential**

Females of childbearing potential must have documentation of a negative pregnancy test prior to dosing.

Females are not considered to be of childbearing potential if they have had a total hysterectomy and/or bilateral tubal ligation or hysteroscopic sterilization (documentation for surgeries must be provided before enrollment) or are in a postmenopausal state (i.e., females who have had cessation of prior occurring menses for  $\geq 24$  months without alternative causes or females with premature ovarian failure).

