#### 4.3.2. Contraception for Male and Female Subjects

All female subjects of childbearing potential and males who are able to father children must agree to abstain from sexual intercourse or to use a highly effective method of birth control during the study and for at least 30 days after the completion of study drug dosing (Section 6.9). A highly effective method of birth control is defined as one that results in a low failure rate (i.e., <1% per year) when used consistently and correctly. Such methods include:

- combined (estrogen and progestogen containing) hormonal contraception associated with inhibition of ovulation
  - oral
  - intravaginal
  - transdermal
- progestogen-only hormonal contraception associated with inhibition of ovulation
  - oral
  - injectable
  - implantable
- intrauterine device (IUD)
- intrauterine hormone-releasing system (IUS)
- bilateral tubal occlusion
- vasectomized partner provided that partner is the sole sexual partner of the female trial participant of childbearing potential and that the vasectomized partner has received medical assessment of the surgical success
- sexual abstinence is considered a highly effective method only if defined as refraining from heterosexual intercourse during the entire period of risk associated with the study treatments. The reliability of sexual abstinence needs to be evaluated in relation to the duration of the clinical trial and the preferred and usual lifestyle of the subject.

NOTE: Birth control methods which are not considered highly effective:

- progestogen-only oral hormonal contraception, where inhibition of ovulation is not the primary mode of action
- male or female condom with or without spermicide
- cap, diaphragm or sponge with spermicide

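### Protocol 6.9 gives the investigator an exception to the negative pregnancy test at entry that Table 1 footnote c, its SAP copy and 4.3.1 do not contain

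*Protocol*

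**What the plan says.** Four places set a pregnancy-test condition for entry or for dosing.

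- **Protocol 6.9** makes a serum test mandatory after a positive urine result ("hCG test must be performed"). Its next sentence reads: "The pregnancy test must be confirmed negative for a subject to be eligible for this study unless the PI deems the test is falsely positive".
- **Protocol Table 1, footnote c** also calls for serum confirmation of a positive urine test, then stops short of the exception: "The pregnancy test must be confirmed negative for a subject to be eligible for this study".
- **SAP Section 4.5, Table 2** (the schedule for Visits 1 to 6) repeats the Table 1 footnote, again with no exception.
- **Protocol 4.3.1** sets a condition on dosing: "Females of childbearing potential must have documentation of a negative pregnancy test prior to dosing". It does not ask for confirmation, and it has no exception.

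Section 6.9 also gives the reason for caution: "TD-9855 demonstrated effects on neonatal mortality and decreased rates of pup growth in the pre- and postnatal study in rats". For the testing schedule it cites Table 1 only. The tests from Week 50 onward are in Protocol Table 2, whose footnote a says: "In women of childbearing potential only, urine beta human chorionic gonadotropin (βhCG) test will be performed".

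**The concern.** An entry criterion that protects against fetal exposure should give the same answer wherever a site looks it up. Here a site working from the schedule of procedures and a site working from Section 6.9 can reach opposite enrolment decisions on the same result. Neither document says which section prevails. Section 6.9 does not say which test may be set aside, on what grounds, or how the judgement is recorded.

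There is also a reporting consequence. SAP 7.3 calls for a listing of all protocol deviations identified before database lock. With two rules in force, whether such an enrolment belongs in that listing depends on which section the person classifying it happens to read.

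**Working it through.** The plan gives no figure on this point and no arithmetic is involved. The check is to set the passages side by side and then run each possible test result through them.

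**Side by side**

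| Place | Decision governed | Condition | Exception |
|---|---|---|---|
| Protocol 6.9 | Eligibility | Confirmed negative | Yes: investigator deems the test falsely positive |
| Protocol Table 1, footnote c | Eligibility | Confirmed negative | None |
| SAP Table 2 footnote (copy of the above) | Eligibility | Confirmed negative | None |
| Protocol 4.3.1 | Dosing | Documented negative | None |

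One of the four places carries the exception and three do not. One of those three is a copy, so there are two separate rules without the exception.

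**Case by case, for a woman of childbearing potential at Week 0**

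1. *Urine negative.* Eligible under 6.9 and footnote c; may be dosed under 4.3.1. The passages agree.
2. *Urine positive, serum negative.* The serum result is the confirmed negative, so 6.9 and footnote c are both met without the exception. A negative test is on file for 4.3.1. The passages agree.
3. *No confirmed negative, and the investigator does not deem the result false.* Ineligible under 6.9 and footnote c; not to be dosed under 4.3.1. The passages agree.
4. *No confirmed negative, and the investigator deems the result false.* Eligible under 6.9, ineligible under footnote c and its SAP copy, and not to be dosed under 4.3.1. The passages conflict.

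The exception changes the outcome only in case 4. That case can arise when the investigator sets aside a positive serum result. It can also arise when a positive urine result is set aside with no negative serum result available, although omitting the serum test altogether would itself breach the preceding sentence of 6.9.

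**Which visit is affected.** The exception qualifies eligibility, and eligibility is decided at Week 0 (inclusion and exclusion criteria are marked only there in Table 1). Dosing begins the day after Visit 1, so the 4.3.1 condition applies between the enrolment decision and the first dose.

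**The case against.** The strongest reply is that the exception is harmless. Serum testing after a positive urine test is mandatory in both 6.9 and footnote c. If the falsely positive test means a urine result that serum has overturned, the two texts agree. That reading is possible and covers the commonest situation. But under it the subject already has a confirmed negative and the exception does nothing; the words have effect only where a confirmed negative is absent.

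A second reply is that the safeguards accumulate. Section 4.3.1 independently bars dosing without a documented negative test, and pregnancy is a stopping reason in Protocol 3.1. This stands. It limits the harm, because a woman enrolled under the exception should still not be dosed. It does not remove the conflict, and it leaves a subject who is eligible by one section and cannot be treated by another.

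Third, the Week 0 test is a Study 0170 Visit 9 procedure, and subjects must continue to meet the 0170 inclusion criteria. The 0170 protocol may settle the matter, but it is not available here.

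A reader might also infer three broader faults, which the documents do not support.

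- *That a positive test after Week 26 needs no serum confirmation, because footnote a of Table 2 is silent.* The serum sentence in 6.9 has no visit limit, and Section 6.1 defines the schedule as Tables 1 and 2 together. What remains is an incomplete cross-reference in 6.9.
- *That most scheduled tests are affected, since most fall under Table 2.* Those tests come after enrolment, where no eligibility decision is made, so counting them does not measure this conflict.
- *That 4.3.1 and 4.3.2 classify the same woman in two ways, because 4.3.1 treats tubal ligation as ending childbearing potential while 4.3.2 lists "bilateral tubal occlusion" as contraception.* The list in 4.3.2 also serves male subjects, for whom a partner's occlusion is a natural entry, so listing it does not show a conflict.

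**Conclusion.** The point holds in a limited form. The eligibility sentence in 6.9 contradicts Table 1 footnote c and its SAP copy, and sits against the dosing condition in 4.3.1, when no confirmed negative exists and the investigator deems the result false. The contradiction is in the text itself and does not depend on any assumption about the population.

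Its size is small. It affects one decision point, in one of the four cases above. The number of women of childbearing potential, and of positive tests among them, is not given; both are assumed small. The SAP Introduction reports 110 subjects enrolled, which caps the number who could have entered under the exception but says nothing about how many did. No such enrolment is documented.

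It would go too far to conclude that the plan permits dosing of a woman with an unresolved positive test. Section 4.3.1 forbids that, and 6.9 requires study drug to be stopped in any pregnant subject.

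**What to change.** Reconcile Protocol 6.9, Protocol Table 1 footnote c, the SAP Table 2 footnote and Protocol 4.3.1 so that a single rule stands in all four places. Which rule stands is for the sponsor to decide. If the exception is kept, 6.9 should say whether it refers to the urine or the serum test, and the other three places should carry it. If it is removed, only the sentence in 6.9 changes. As a minor clean-up, 6.9 should cite Table 2 alongside Table 1 for the testing schedule.

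The cost is wording, with no new procedure. Because the SAP says the sponsor terminated the study early, the remaining practical value is a settled rule for classifying any such enrolment in the SAP 7.3 deviation listing, and corrected text before this protocol is reused.
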